## 8.3 STATISTICAL ANALYSIS

Summary statistics, including mean, standard deviation and 95% confidence interval, will be used to describe the ORR. Kaplan-Meier curve will be used to estimate the PFS. We will calculate mean, standard deviation and 95% confidence interval of PFS6 and median PFS. Safety will be assessed by reporting the grades of toxicity and the type of toxicity observed for all patients and summarizing data using the descriptive statistics, including mean, standard deviation and confidence intervals.

*Abbreviated Title: Ph II Sunitinib CNS Sarcomas*

*Version Date: 05-30-18*

Treatment effect of sunitinib will be evaluated using advanced MRI of the brain. Perfusion and diffusion-based MRI parameters including but not restricted to blood volume, mean and median ADC and structural volumes will be analyzed. Results will be summarized, and mean and median values at different time points will be tabulated. Changes in such parameters will be checked for statistical significance and correlated with the disease status. The relationship between biomarkers and response will be evaluated using Spearman correlation and regression analysis; the levels of biomarkers will be compared between responders and non-responders using an exact Wilcoxon rank sum test and t test.

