#### 1.2.1 Gliosarcoma

Gliosarcoma, tumor classified as a rare variant of glioblastoma, demonstrates biphasic glial and mesenchymal differentiation. Primary gliosarcoma is a de novo neuroepithelial tumor that exhibits dual glial and sarcomatous components at initial diagnosis.[\[1\]](#) On occasion, glioblastoma in the recurrent setting may transition from typical glial phenotype (GFAP positive) to a tumor with reticulin rich sarcomatous-mesenchymal features (secondary gliosarcoma). These tumors are more common in men and often arise in the temporal lobes. While extra-cranial metastasis from glioblastoma is rare, gliosarcomas have a propensity to disseminate extra-cranially likely due to the sarcomatous component. Patients with gliosarcoma experience poor outcome with median survival ranging from 4 to 24 months.[\[2, 3\]](#)

**Abbreviated Title:** Ph II Sunitinib CNS Sarcomas

**Version Date:** 05-30-18

The underlying tumor biology of gliosarcoma appears to be distinct compared to glioblastoma. Frequency of *TP53* mutation is higher and only on very rare occasion EGFR amplification is present. In addition, MGMT methylation and IDH mutations are rare in gliosarcomas.[\[3\]](#) Most patients that present with gliosarcoma are treated similarly to those with glioblastoma in spite of the likely differences in tumor pathogenesis and therefore therapeutic response pattern. Treatment options for patients with recurrent gliosarcoma are extremely limited. However, gliosarcomas often possess platelet-derived growth factor receptor (PDGFR), KIT/ SCF autocrine activation loops, suggesting the potential utility of certain tyrosine kinase inhibitors.[\[4\]](#)

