### 1.2.2 Primary CNS sarcoma

Primary sarcomas of the CNS are rare tumors (~1.5% of all intracranial tumors) with little known concerning the underlying biology. They are believed to arise from mesenchymal tissues within the intracranial cavity such as blood vessels, meninges, or bone. As such, these tumors are histologically similar to sarcomas of soft tissue or bone. The current WHO classification recognizes specific differentiation: fibrosarcoma, solitary fibrous tumor, chondrosarcoma, osteosarcoma, liposarcoma, inflammatory malignant myofibroblastic tumor, leiomyosarcoma, rhabdomyosarcoma, angiosarcoma, and other CNS sarcomas. Although detailed studies of these tumors are limited, reports indicate they may be in part driven by vascular endothelial growth factor (VEGF).[\[5\]](#) Treatment consists of surgical resection when accessible, followed by irradiation. There are no known effective medical therapies for primary CNS sarcomas.

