### **3 STUDY IMPLEMENTATION**

#### **3.1 STUDY DESIGN**

This is a prospective, single institution, single arm, multi-cohort phase II study of sunitinib in subjects with recurrent gliosarcoma and primary CNS sarcoma that have failed prior surgery and irradiation (unless radiation therapy was contraindicated). Subjects will be classified into three cohorts: 1) Primary gliosarcoma; 2) Secondary gliosarcoma; 3) Primary CNS sarcoma. Cohort expansion will be carried out at indication of promising response.

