## 8 STATISTICAL CONSIDERATIONS

### 8.1 GENERAL APPROACH

We monitor the ORR using the Bayesian optimal phase 2 (BOP2) design [18]. Specifically, let  $n$  denote the interim sample size and  $N$  denote the maximum sample size. Let  $p$  denote the ORR and define the null hypothesis  $H_0: p \leq 0.2$ , representing that the treatment is ineffectual. We will stop enrolling patients and claim that the treatment is not promising if

$$Pr(p > 0.2 | data) < \lambda \left(\frac{n}{N}\right)^\alpha,$$

where  $\lambda=0.85$  and  $\alpha=0.8$  are design parameters optimized to minimize the chance of incorrectly claiming that an efficacious treatment is not promising (i.e., type II error) under the alternative hypothesis  $H_1: p = 0.4$ , while controlling the type I error rate at 0.1 (i.e., the chance of incorrectly claiming that an ineffectual treatment is promising is no more than 10%).

Assuming a Beta(0.2,0.8) prior distribution for  $p$ , the above decision rule corresponds to the following stopping boundaries and yields a statistical power of 0.8537 under  $H_1$ :

**Table 1.** Stopping boundaries

# patients treated	Stop if # responses <=
16	3
24	5
32	9

Based on Table 1, we perform the interim and final analysis when the number of enrolled patients reaches 16, 24 and 32. If the number of responses fails to exceed the stopping boundary, we will suspend accrual, inspect the efficacy data and make the go/no-go decision based on both the ORR and other clinical considerations (e.g., PFS).

*Abbreviated Title: Ph II Sunitinib CNS Sarcomas*

*Version Date: 05-30-18*

Below are the operating characteristics of the design based on 10000 simulations using the BOP2 web application, which is available at <http://www.trialdesign.org>.

ORR	Early stopping (%)	Claim promising (%)	Sample size
0.1	97.95	0.05	16.7
0.2	71.74	8.00	21.5
0.3	31.45	46.22	27.5
0.4	7.92	85.37	30.8
0.5	1.31	98.13	31.8

We monitor the rate of Dose Limiting Toxicity (DLT) independently for each cohort using the following Bayesian rule: stop enrolling patients to a cohort if  $\text{Pr}(\text{DLT} > 30\% \mid \text{data}) > 0.9$ . That is, we will stop enrolling patients to a cohort if the data indicate that there is more than 90% chance that the true DLT rate is higher than 30%. This posterior probability is calculated based on the beta-binomial model. The decision rule gives the following stopping rule, assuming a Beta(0.1, 0.4) prior distribution for DLT rate,

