## 8.2 SAMPLE SIZE JUSTIFICATION

With the maximum sample size of 32 patients per cohort, the 95% confidence interval of the estimated ORR will not be wider than 0.19 in each direction. At the two-sided significance level of 0.2, we have 80% power to detect the ORR of 48% versus 30%.

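### The biomarker tests of responders against non-responders carry no cohort factor, so if they are run across cohorts a marker of histology can pass for a marker of response whenever response rates also differ by cohort

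*Combined protocol and SAP*

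**What the plan says.** Section 8.3 is the only place that describes the biomarker analysis. It states that "The relationship between biomarkers and response will be evaluated using Spearman correlation and regression analysis" and that "the levels of biomarkers will be compared between responders and non-responders using an exact Wilcoxon rank sum test and t test". It names no stratum, covariate or by-cohort rule for any of these methods, and no other section supplies one.

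The design in section 3.1 has three groups: "Subjects will be classified into three cohorts: 1) Primary gliosarcoma; 2) Secondary gliosarcoma; 3) Primary CNS sarcoma". Cohort is assigned at registration (section 2.3.1). Section 8.2 sizes the trial by cohort ("With the maximum sample size of 32 patients per cohort"), and section 8.1 monitors dose-limiting toxicity separately in each cohort. Section 3.1 adds: "Cohort expansion will be carried out at indication of promising response".

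Two secondary objectives in section 1.1.2 depend on this analysis. One examines sunitinib-targeted pathways in archival tissue as possible biomarkers of response. The other looks for new ones by broad molecular profiling.

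**The concern.** A rank sum test or t test with responder status as its only factor cannot separate two explanations of a positive result: that the marker tracks response among patients of the same histology, or that the marker is higher in the histology that happened to respond more. The second is confounding by cohort. It needs two things at once: marker levels that differ between cohorts, and ORRs that differ between cohorts.

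The documents make both possible, though they establish neither. On markers, section 1.2.1 says that "gliosarcomas often possess platelet-derived growth factor receptor (PDGFR), KIT/ SCF autocrine activation loops", while section 1.2.2 suggests, tentatively, that primary CNS sarcomas may depend partly on VEGF. Broad profiling is also likely to pick up markers of histology. On response, expansion that depends on promising results allows for some cohorts responding and others not, and it ties cohort size to response.

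At stake is whether a reported biomarker of response is more than a label for histology. A real within-cohort relation could also be masked. The problem arises for a single pre-chosen marker, so a multiplicity correction would not cure it.

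**Working it through.** **1. The plan's own figures.** The documents give no figure for the biomarker comparison, so the check starts from the ORR design in section 8.1. The rule Pr(p > 0.2 | data) < 0.85(n/32)^0.8 with a Beta(0.2, 0.8) prior has thresholds 0.488, 0.675 and 0.85 at n = 16, 24 and 32. These give boundaries of 3, 5 and 9 responses, as stated. Exact binomial recursion gives power 0.8555 at ORR 0.4 (stated 0.8537) and a promising rate of 0.0807 at ORR 0.2 (stated 8.00%). The design reproduces, so its stopping boundaries can be used below.

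**2. Inputs.**
- From the documents: three cohorts, at most 32 each; ORR 0.2 (null) and 0.4 (alternative); stopping boundaries 3/16 and 5/24.
- Assumed: cohort ORRs that differ (including 0.1 and 0.3), marker shifts of 0.5 to 1 SD between cohorts, a two-sided 5% level, and the ORR boundaries applied in each cohort.
- Under test: a marker with SD 1 that is independent of response within every cohort, so every rejection is a false positive for a biomarker of response.

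**3. Size of the spurious difference.** With equal cohort sizes, cohort means μ_k and response rates p_k, the expected responder minus non-responder difference is

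Δ = Σ μ_k p_k / Σ p_k − Σ μ_k (1 − p_k) / Σ (1 − p_k).

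For means 0/0/1 SD:
- ORR 20/20/20%: 0.2/0.6 − 0.8/2.4 = 0.333 − 0.333 = 0.
- ORR 30/30/40%: 0.4/1.0 − 0.6/2.0 = 0.10 SD.
- ORR 20/20/40%: 0.4/0.8 − 0.6/2.2 = 0.500 − 0.273 = 0.23 SD.
- ORR 10/20/40%: 0.4/0.7 − 0.6/2.3 = 0.571 − 0.261 = 0.31 SD.

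So a marker that differs between cohorts produces no spurious difference when ORRs are equal.

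**4. False-positive rates with every cohort at 32.** The stratified comparator is the van Elteren test, Z = Σ w_k[W_k − n_1k(n_k + 1)/2] / √{Σ w_k² n_1k n_0k (n_k + 1)/12}, with w_k = 1/(n_k + 1). Here W_k is the responders' rank sum within cohort k, and n_1k and n_0k are the numbers of responders and non-responders. Normal-approximation p-values were used; 3,000 simulated trials per row.

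| ORR by cohort | Shift in third cohort | Pooled Wilcoxon | Stratified |
|---|---|---|---|
| 20/20/20% | 1.0 SD | 4.5% | 4.7% |
| 30/30/40% | 1.0 SD | 7.6% | 4.8% |
| 20/20/40% | 0.5 SD | 6.5% | 4.5% |
| 20/20/40% | 1.0 SD | 14.5% | 4.9% |

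The pooled t test behaves almost identically (14.9% in the last row).

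**5. With the planned stopping.** Cohorts with low ORR rarely reach 32. Section 8.1 gives mean sizes of 16.7, 21.5 and 30.8 at ORR 0.1, 0.2 and 0.4, so a 10/20/40% trial averages 16.7 + 21.5 + 30.8 = 69.0 patients, not 96. With the 3/16 and 5/24 boundaries applied in each cohort and a 1 SD spread in marker means (0/0.5/1 or 0/0/1):

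| ORR by cohort | Pooled Wilcoxon | Stratified |
|---|---|---|
| 10/20/40% | about 13–17% | about 5% |
| 20/20/40% | about 9–13% | about 5% |
| 30/30/40% | about 6–7% | about 5% |
| equal ORRs | about 5% | about 5% |

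Simulation error is about half a point to a point (with 4,000 trials, √(0.15 × 0.85/4000) = 0.6 points), and a repeat of the largest contrast gave 18%. With shifts of only 0.5 SD the rate is about 7–9% at the wider ORR contrasts and close to nominal at 30/30/40%.

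**The case against.** The strongest reply is that silence is not a choice of pooling. Section 8.3 does not say whether any of its analyses are by cohort or overall, while sections 8.1 and 8.2 use by-cohort language for toxicity monitoring and sample size. Testing within each cohort is a fair reading and carries no between-cohort confounding. The regression names no covariates, so a cohort term is not excluded. This stands: the defect is that cohort handling is unstated, and a reader who infers that the plan prescribes pooling goes beyond the text. It does not remove the point, because the named tests have no place for cohort and the wording permits running them on all patients.

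Four other inferences are tempting and unsupported.
- That a histology difference in the marker is enough. It is not; ORR must differ too.
- That the cohorts were formed because biology and response were expected to differ. Sections 2.3.1 and 3.1 define the cohorts without giving that reason. The background neither compares the entities on these pathways nor says that a pathway named for one is absent in the other.
- That the false-positive rate is 18 to 21%. Figures of that size arise for ORR 10/20/40% with a 1 SD spread when all cohorts are held at 32, which ignores the stopping rule.
- That the trial's main conclusion is at risk. The ORR design, for which section 8.1 speaks of "controlling the type I error rate at 0.1", makes no use of the biomarker tests.

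The objectives concerned are secondary and seek only candidate biomarkers, and section 8.3 sets no significance level for them. That limits the weight of the point.

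**Conclusion.** The point holds conditionally. If the section 8.3 tests are run across the three cohorts, and both marker level and ORR differ between cohorts, the chance of declaring a marker of response that has no within-cohort relation to response is about 6 to 17%, against about 5% when stratified. With equal ORRs, or with tests run within cohort, there is no inflation.

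The range rests on assumed marker differences of 0.5 to 1 SD, assumed cohort ORRs, an assumed 5% level, and stopping boundaries applied per cohort. It describes the scenarios examined and is not a bound. Weak contrasts are close to nominal; wider ones exceed it (ORR 10/10/40% with a 1 SD shift and cohorts fixed at 16, 16 and 32 gives 23%).

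This is worth correcting before the analysis, for the secondary biomarker objectives only. The primary ORR result and the stopping rules are unaffected.

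**What to change.** Add to section 8.3:

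> Comparisons of biomarker levels between responders and non-responders will be stratified by cohort (for example a van Elteren test, or a permutation test within cohort). Regression models relating biomarkers to response will include cohort. Rank correlations will be adjusted for cohort or reported within cohort.

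Plots of marker level against response within each cohort would let readers see whether a relation recurs across histologies. If the intention was always to test within each cohort, one sentence saying so also resolves the point.

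The cost is a change of wording, since cohort is already recorded at registration. When cohorts do not differ, stratifying loses about 1 to 2 points of power (for example 81% to 79% with 32 per cohort, ORR 25% and a 0.7 SD effect). A cohort with few responders contributes little: 16 patients at ORR 10% give an expected 16 × 0.1 = 1.6 responders. Permutation p-values are therefore preferable to the normal approximation in small strata.

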#### 1.1.3 Exploratory:

- Blood will be collected to evaluate presence of and changes to circulating VEGFR2, PLGF, IL-4, IL-12, HGF, basic FGF, circulating tumors cells, endothelial progenitors, mature apoptotic endothelial cells, regulatory T cells, exhausted CD8 T cells, myeloid-derived suppressor cells (MDSC), and Th1/Th2 T cells. Immunophenotyping evaluations will be performed upon availability of tumor samples.
- To assess free-living physical activity and sleep quality (Optional).

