### 1.2.5 Rationale for Exploratory Studies

Serum markers of angiogenesis: A potential mechanism for sunitinib resistance is the upregulation of alternative proteins and/or pathways that could drive tumor angiogenesis and/or growth independent of VEGF. Preclinical studies, involving RCC and non-RCC models have identified a variety of candidate proteins that may be involved in resistance to VEGF therapy. Among these proteins which stimulate angiogenesis directly or indirectly are fibroblast growth factor (FGF), hepatocyte growth factor (HGF), and placental growth factor (PlGF). We propose to explore the potential utility of these proteins as biomarkers of pharmacological and clinical activity of sunitinib in CNS sarcomas. These assays will be performed in the [name] Laboratory, DTB, NCI.

Peripheral blood immune monitoring: In addition to modulation of angiogenic activity, sunitinib also appears to regulate key anti-tumor immune response. Sunitinib has been shown to decrease the frequency of regulatory T cells (Tregs) and myeloid-derived suppressor cells (MDSCs) in metastatic renal cell carcinoma patients.[8, 9] It has been shown that development of sunitinib resistance is partly mediated by the survival of MDSCs, thereby providing sustained immune suppression and angiogenesis.[10] Sunitinib has also shown to shift T-helper cells toward a T helper 1 (Th1)-polarized response and increase the Th1 cell / T helper 2 (Th2) cell ratio. A significant decrease in the Th1/Th2 ratio was seen after sunitinib treatment in the PFS-short group in mRCC.[9, 11] Exhausted CD8+ T cells which express inhibitory receptors PD-1 and Tim-3 were found in cancer patients, and therapeutic response was correlated with decline in Tim-3+ CD8+ T cells. Peripheral blood will be collected into one 8 ml CPT tube. Peripheral blood mononuclear cells (PBMC) will be assessed using multiparameter flow cytometry for immune subsets including but not necessarily limited to CD8+ T-cells, CD4+Foxp3- T-cells, Tregs, monocyte subsets, MDSC subsets. Assessment will include functional markers, i.e. PD-1, Tim-3, CTLA-4, PD-L1, HLA-DR and/or CD40. Therefore, monitoring immune subsets in CNS sarcoma patients pre- and post-sunitinib therapy may contribute to improved understanding of sunitinib and possibly inform future studies.

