Circulating Endothelial Cells (CEC) and Endothelial Progenitor Cells (CEP): CECs have emerged as a potentially useful marker to assess anti-angiogenic therapy. At least two distinct populations of CECs have been identified, bone marrow-derived CEP cells and mature CECs. CEP cells bear antigens that identify them as endothelial cells, such as VEGFR2 (Flk-1) and CD31, as well as antigens for stem cells, such as CD117, CD133, and CD34. Upon appropriate stimulation, bone marrow-derived endothelial progenitor cells migrate to the circulation, where they are referred to as CEP cells. CEP cells have been shown to infiltrate human tumors and give rise to tumor neovasculature. Further VEGFR signaling is thought to mobilize CECs which is consonant with the observation that CECs are increased in patients with active cancer. How sunitinib may affect CECs and CEPs is unclear. To explore this, pre-treated and post-treated samples will be obtained to perform CEC/CEP analyses by multi-parametric flow cytometry in the [name] Laboratory.

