### 3.5 STUDY CALENDAR

Procedure	Screening/ Baseline	Cycle 1			Subsequent Cycles		End of treatment Visit 	Post Therapy Follow- up
		Day 1	Day 8	Day 15	Day 1	Day 15		
		+/- 3			+/- 3	+/-3		
History and PE	X	X	X		X		X	
Vital signs	X	X	X		X		X	
Performance Score (KPS)	X	X	X		X		X	X
CBC w/diff, plts	X	X	X		X		X	
Serum chemistry 	X	X	X		X		X	
Urinalysis	X							
PT/PTT INR	X							
Thyroid function tests 	X				X		X	
β-HCG (serum or urine)	X							
Blood Pressure	X	X	X	X	X	X	X	
Correlative Research Studies 		X	X		X		X	
MDASI-BT 	X						X	
Cranial MRI/CT 	X						X	
EKG/ECHO 	X							
Adverse Events 		X					→	
Concomitant Medications 	X	X			X			
Actigraphy 	X	X	X	X	X	X		
NIH Advanced	X							

*Abbreviated Title: Ph II Sunitinib CNS Sarcomas*

*Version Date: 05-30-18*

Procedure	Screening/ Baseline	Cycle 1			Subsequent Cycles		End of treatment Visit 	Post Therapy Follow- up
		Day 1	Day 8	Day 15	Day 1	Day 15		
Directives Form 								

*Total protein, albumin, calcium, phosphorus, magnesium, glucose, BUN, creatinine, sodium, potassium, alkaline phosphatase, ALT, AST, total bilirubin, direct bilirubin*

*Thyroid function tests to be done at baseline, C2D1, D1 of every other cycle and at end of treatment visit*

*Blood for correlative studies will be collected at C1D1, C1D8, C2D1 and at end of treatment visit*

*MDASI-BT to be done at baseline, at time of imaging studies throughout treatment, and at end of treatment visit*

*Response assessment to be done every other cycle within 7 days of initiation of odd numbered cycles, starting with Cycle 3 and at end of treatment visit. (Pre C1 MRI is done at screening. MRI is preferred.)*

*ECHO to be done at screening, day 1 of cycle 3 and every other cycle EKG/ECHO frequency of day 1 of the third cycle and every other cycle.*

*Adverse Event and Concomitant Medication evaluations to be documented at day 1 of each cycle and at end of treatment visit*

*ActiGraphy to be done at baseline and during cycles 1 through 6*

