## 5 BIOSPECIMEN COLLECTION

### 5.1 CORRELATIVE STUDIES FOR RESEARCH

Test/assay	Volume blood (approx)	Type of tube	Collection point (+/- 48hrs)	Location of specimen analysis
Circulating mature endothelial cells and endothelial progenitor cells Immune-monitoring	8 ml at C1D1, C1D8, C2D1	CPT citrate (blue/black)	C1D1, C1D8, C2D1 and at end of treatment visit	[name] Lab
Circulating tumor cells	7.5 ml at C1D1, C1D8, C2D1	CellSave tube	C1D1, C1D8, C2D1 and at end of treatment visit	[name] Lab
Immune subset analyses	8 ml at C1D1, C1D8, C2D1	CPT citrate (blue/black)	C1D1, C1D8, C2D1 and at end of treatment visit	[name] Lab

For [name] Lab samples, contact the lab by email: [name] ([[contact]](mailto:[contact])), [name] ([[contact]](mailto:[contact])), [name] ([[contact]](mailto:[contact])), and [name]

*Abbreviated Title: Ph II Sunitinib CNS Sarcomas*

*Version Date: 05-30-18*

([[contact]](mailto:[contact])) when the patient is scheduled and by phone at [contact] when the blood has been drawn, and a [name] Lab member will come to pick it up. Store at ambient temperature. The samples will be 2D barcoded, securely stored at the appropriate temperature, and entered into a secure patient database that can only be accessed by laboratory members. Each laboratory member can only interact with the database at their approved level of access. All laboratory members have completed courses in patient information security and computer security. Samples will only be released with approval of the Principal Investigator. No cell lines will be established.

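### Section 8.3 names no within-patient analysis for the serial blood markers, although the exploratory objective and the sampling schedule are about change on sunitinib

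*Combined protocol and SAP*

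**What the plan says.** The exploratory objective (section 1.1.3) has two parts, presence and change: "Blood will be collected to evaluate presence of and changes to circulating VEGFR2", followed by a list of further markers and cell types.

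The rationale (section 1.2.5) is also longitudinal. For immune subsets, "monitoring immune subsets in CNS sarcoma patients pre- and post-sunitinib therapy may contribute to improved understanding of sunitinib", and the evidence cited is that "therapeutic response was correlated with decline in Tim-3+ CD8+ T cells". For circulating endothelial cells and their progenitors, the effect of sunitinib is described as unknown, and "pre-treated and post-treated samples will be obtained to perform CEC/CEP analyses".

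The schedule fits that aim. A footnote to the study calendar (section 3.5) says "Blood for correlative studies will be collected at C1D1, C1D8, C2D1 and at end of treatment visit", and the table in section 5.1 gives the same times.

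The analysis text is in section 8.3: "The relationship between biomarkers and response will be evaluated using Spearman correlation and regression analysis", and then "the levels of biomarkers will be compared between responders and non-responders using an exact Wilcoxon rank sum test and t test". It does not say which sampling time supplies the level. It defines no change from baseline, baseline covariate, paired test or repeated-measures model for blood markers. The one sentence in section 8.3 about testing change refers to the MRI parameters described just before it.

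**The concern.** The samples are repeated measures on the same patient, and each patient's C1D1 value is the natural reference. Every method stated for biomarkers instead has response as the other variable. A marker that rises equally in all patients would show no association with response, so the plan could not detect the effect that the blood draws are meant to look for.

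There is a second, conditional problem. If the levels compared are on-treatment levels, a difference between responders and non-responders may have existed before the first dose. Without the C1D1 value in the analysis, it could be read as a differential effect of the drug. Part of the between-patient variation that C1D1 could explain also stays in the error term.

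**Working it through.** **The plan's own figures.** The documents give no power or sample size for biomarkers, so there is no biomarker figure to reproduce. The design inputs borrowed below do check out. The stopping boundaries 3/16, 5/24 and 9/32 follow exactly from the Beta(0.2, 0.8) prior with λ = 0.85 and α = 0.8. Exact power at a response rate of 0.4 is 0.8555, against the stated 0.8537 from simulation.

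**Inputs.**
- From the documents: a maximum of 32 per cohort (section 8.2) and a response rate of 0.4 under H1 (section 8.1). 0.4 × 32 = 12.8, so 13 responders and 19 non-responders.
- Assumed, because the documents are silent: analysis within one full cohort; markers normal with SD 1 at each time on the analysis scale; two-sided 0.05; pre/post correlation ρ from 0.3 to 0.8 (to 0.9 in part 1); effects in SD units.

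**1. Can the stated group test detect change on drug?** Let every patient change by 0.8 SD, with 10 responders and 22 non-responders. By simulation over ρ = 0.5-0.9, the rank sum test on post-treatment levels rejects in about 5% of runs, which is its alpha. A signed-rank test on the same pairs rejects in 99-100%.

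**2. A baseline gap with equal change in both groups.** Let responders start 0.5 SD higher. The standard error factor is √(1/13 + 1/19) = 0.360.
- Levels: noncentrality 0.5/0.360 = 1.39, rejection about 27%; simulation gives 25-28% over the range of ρ.
- C1D1 covariate: the adjusted difference is 0.5(1 − ρ) and the residual SD is √(1 − ρ²). At ρ = 0.5 these are 0.25 and 0.866, so noncentrality is 0.25/(0.866 × 0.360) = 0.80. Simulated rejection is about 11%, ranging from about 16% (ρ = 0.3) to 7% (ρ = 0.8).
- Change from C1D1: the gap cancels, and rejection is about 5%.

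**3. A true 0.8 SD difference in change, no baseline gap.** Noncentrality is 0.8/(SD × 0.360). The SD is 1 for levels, √(2(1 − ρ)) for change scores and √(1 − ρ²) with the C1D1 covariate. At ρ = 0.5 the values are 2.22, 2.22 and 2.57.

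| ρ | Levels | Change from C1D1 | C1D1 covariate |
|---|---|---|---|
| 0.3 | 0.55-0.58 | 0.44-0.45 | about 0.61 |
| 0.5 | 0.55-0.58 | 0.57 | 0.68 |
| 0.8 | 0.55-0.58 | 0.92 | 0.94 |

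In the levels column the lower end is the Wilcoxon test and the upper end the t test. With a 10/22 split and ρ = 0.5, the noncentral-t values are 0.53 for levels and 0.65 with the covariate.

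**The case against.** The best defence is that section 8.3 is brief rather than wrong.

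- **The two-group tests are not the only methods named.** Spearman correlation and regression come first, and the remedy for the response comparison is itself a regression. This stands. But both are aimed at response, and no baseline or change term is given.
- **A rank sum test on levels is a sound method for its own question.** The secondary objectives (section 1.1.2) look for biomarkers of response in archival tissue, which is measured once, and C1D1 blood is also a single value. This stands too.
- **A reader might infer that baseline confounding is built into the plan.** The documents do not support that. It arises only if on-treatment levels are compared without adjustment, and the sampling time is left open.
- **A reader might infer that power is always lost.** That is also too strong. Below ρ = 0.5 raw change scores do worse than levels, and the gain from the covariate depends on a correlation that the plan does not give. Nor is it fair to charge the plan with the low power of an unpaired pre-versus-post test, since it proposes none.
- **The adjusted regression is not free of baseline effects.** It rejects in about 11% of runs in part 2. That is why the change-score result should be reported beside it.
- **More tests follow.** Section 1.1.3 lists about 13 markers; with two time points and three analyses, 13 × 2 × 3 = 78 tests.

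What remains is that no stated method addresses change in blood markers, and that a C1D1 value already collected goes unused.

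**Conclusion.** The point holds as a missing analysis and an undefined time point. The objective, rationale and schedule set a within-patient question for circulating markers, and section 8.3 names no analysis that answers it.

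The size is illustrative. For a 0.8 SD difference in change with a 13/19 split, power moves from about 0.55-0.58 on levels to about 0.61, 0.68 and 0.94 with the C1D1 covariate at ρ = 0.3, 0.5 and 0.8. The correlations, effect sizes, normality and a full cohort of 32 are assumptions, and fewer responders would lower every figure.

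The severity is minor. The markers are exploratory, and no sample size or decision rule rests on them. The objective-response-rate rule uses one binary outcome per patient and is not touched.

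**What to change.** In section 8.3, keep the comparison of levels for markers measured once (archival tissue, C1D1 blood). For the serial blood markers, add the following, labelled exploratory:

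1. State the time points, and test within-patient change from C1D1 to C1D8 and from C1D1 to C2D1 with a Wilcoxon signed-rank test. Use the log scale where values are positive, and the original scale for markers that can be zero, such as circulating tumor cells.
2. Compare responders with non-responders by regressing the on-treatment level at each of those times on response status, with the C1D1 level as covariate. Report the comparison of change from C1D1 beside it, because the adjusted analysis keeps part of any baseline gap.
3. Summarise the end-of-treatment sample descriptively, and state that p-values are not adjusted for multiplicity.

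The cost is wording in the analysis section; every sample is already scheduled. The downsides are that patients without a C1D1 sample drop out of the serial analyses, and that there are more exploratory tests to report.
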